Progression-free survival will be right-censored for subjects who met one of the following conditions: 1) no baseline disease assessments, 2) non-protocol anti-myeloma therapy started before documentation of disease progression or death, 3) death or disease progression immediately after more than 1 consecutively missed disease assessment visit, or 4) alive and does not have documentation of disease progression before a data analysis cutoff date. These conventions are based on the May 2007 FDA Guidance for Industry, 'Clinical Trial Endpoints for the Approval of Cancer Drugs and Biologics' (https://www.fda.gov/downloads/Drugs/Guidances/ucm071590.pdf), The censoring rules for the primary analysis of PFS are described in Table 5-1. Additionally, if the last disease assessment date is after the date that triggers the analysis, the subject will be censored at the analysis trigger date.

Date: 08 June 2018 Page 13 of 27

Table 5-1 Conventions for Censoring for PD dates

	Date of Progression or	
Situation	Censoring	Outcome
No baseline disease assessments	Date of first dose	Censored
New anti-myeloma therapy started	Date of last disease assessment	Censored
before documentation of PD	prior to start of new	
or death	anti-myeloma therapy	
Death or PD immediately after	Date of last disease assessment	Censored
more than 1 consecutively	visit without documentation of PD	
missed disease assessment visit	that is before the first missed visit	
Alive and without PD	Date of last disease assessment	Censored
documentation (including lost to		
follow-up without PD)		
Death or PD between planned	Date of death or first disease	Progressed
disease assessments	assessment showing PD,	
	whichever occurs first	
Death before first disease	Date of death	Progressed
assessment		

Treatment-emergent Adverse Event

AEs starting on or after first dose of investigational product as indicated by field "*Did* event start before first dose of investigational product?" in Events page and up to 30 days, inclusive, after the last dose of study treatment.

6. Analysis Sets

6.1 Full Analysis Set

The full analysis set will include all enrolled subjects who received at least 1 dose of any study treatment (ie, carfilzomib or dexamethasone).

6.2 Safety Analysis Set

The safety analysis set is the same as full analysis set.

Date: 08 June 2018 Page 14 of 27

6.3 Interim Analyses Set(s)

Not Applicable.

7. Planned Analyses

7.1 Interim Analysis and Early Stopping Guidelines

Not Applicable.

7.2 Primary Analysis

Not Applicable.

7.3 Final Analysis

The final analysis will occur after all subjects have completed therapy, disease assessment and safety follow-up.

8. Data Screening and Acceptance

8.1 General Principles

The objective of the data screening is to assess the quantity, quality, and statistical characteristics of the data relative to the requirements of the planned analyses.

8.2 Data Handling and Electronic Transfer of Data

The Amgen Global Study Operations-Data Management (GSO-DM) department will provide all data to be used in the planned analyses. This study will use the RAVE database.

8.3 Handling of Missing and Incomplete Data

The descriptive statistics will identify the extent of missing data. Rules for handling missing data related to endpoints are described in the endpoint definitions or in the description of analyses. The handling of incomplete and partial dates for adverse events and concomitant medications are described in Appendix A.

8.4 Detection of Bias

Not Applicable.

8.5 Outliers

Any suspected outliers will be investigated by the study team and will be included in the database unless determined to be an error or there is supporting evidence or explanation to justify the exclusion. Any outliers excluded from the analysis will be discussed in the Clinical Study Report (CSR), including the reasons for exclusion and the impact of their exclusion on the study.

Date: 08 June 2018 Page 15 of 27

8.6 Distributional Characteristics

The statistical assumptions for analysis methods will be assessed. If the assumptions for the distributional characteristics are not met, these will be described and further analyses may be carried out using data transformations or alternative analysis methods. The use of transformations or alternative analysis methods will be justified in the final study report.

8.7 Validation of Statistical Analyses

Programs will be developed and maintained, and output will be verified in accordance with current risk-based quality control procedures.

Tables, figures, and listings will be produced with validated standard macro programs where standard macros can produce the specified outputs.

The production environment for statistical analyses consists of Amgen-supported versions of statistical analysis software; for example, the SAS System version 9.4 or later.

9. Statistical Methods of Analysis

9.1 General Considerations

In general, safety analysis set will be utilized to generate summary statistics for different dosing regimen, including Kyprolis in combination with dexamethasone (Kd) 56 mg/m² [Kd56] twice weekly and Kd 70 mg/m² [Kd70] weekly.

Continuous variables will be summarized by the non-missing sample size (n), mean, standard deviation, median, minimum, and maximum. Categorical variables will be summarized by the n and percentage in each category. Time to event endpoints will be summarized with Kaplan-Meier (KM) curves (Kaplan and Meier, 1958), KM proportions at select time points, KM quartiles (when estimable), the number of subjects with events, the number of subjects censored, and censoring reasons. Point estimates for efficacy endpoints will be accompanied by 2-sided 95% confidence intervals including estimates of KM quartiles (Klein and Moeschberger, 1997), KM proportions (Kalbfleisch and Prentice, 1980), and binomial proportions (Clopper CJ and Pearson, 1934).

9.2 Subject Accountability

The number and percent of subjects who were screened, enrolled, and received study treatment will be summarized. The number and percent of subjects who discontinued study treatment and study will also be tabulated, along with the reason for

Date: 08 June 2018 Page 16 of 27

discontinuation. Key study dates for the first subject enrolled, last subject enrolled, and data cut-off date for analysis will be presented.

9.3 Important Protocol Deviations

Important Protocol Deviations (IPDs) categories are defined by the study team before the first subject's initial visit and updated during the IPD reviews throughout the study prior to database lock. These definitions of IPD categories, subcategory codes, and descriptions will be used during the course of the study. Eligibility deviations are defined in the protocol.

9.4 Demographic and Baseline Characteristics

Descriptive statistics for demographic and baseline characteristics will be summarized.

Baseline demographics and characteristics:

- age (as categorical variable: 18 to < 65, 65 to 75, and > 75 years)
- sex (male, female)
- race (white and other categories depending on frequency observed)
- commute distance to treatment center: 0-10, 11-25, > 25 miles

Baseline organ function and comorbid conditions:

- ECOG performance status (0 or 1)
- estimated GFR (< 50 vs ≥ 50 mL/min/1.73 m²)
- hypertension history (include use of anti-hypertensive medications) (yes, no)
- history of ischemic heart disease (myocardial infarction or coronary artery disease), congestive heart failure (NYHA class ≤ 2), stroke, or history of peripheral vascular disease (yes, no)
- family history of coronary artery disease in first degree relatives with onset
 4 65 years of age for female relative or
 55 years of age for male relative (yes, no)
- smoking history (yes, no)
- history of hyperlipidemia (yes, no)
- history of diabetes (yes, no)
- history or chronic mild hepatic impairment (yes, no)

Baseline disease characteristics:

- revised international staging system stage (stage 1 vs stage 2 vs stage 3 vs unknown)
- determination of measurable disease at baseline (based on serum or urine M-protein, based on SFLC only)
- β2-microglobulin level (< 2.5, ≥ 2.5 and < 5.5, ≥ 5.5 mg/L)

Date: 08 June 2018 Page 17 of 27

- presence of soft tissue plasmacytoma (yes, no)
- progressive disease on lenalidomide during or within 60 days of treatment (yes, no)
- progressive disease on lenalidomide in combination with dexamethasone during or within 60 days of treatment (yes/no)

9.5 Efficacy Analyses

9.5.1 Analyses of Primary Efficacy Endpoint(s)

Not applicable.

9.5.2 Analyses of Secondary Efficacy Endpoint(s)

European Organization for Research and Treatment of Cancer Quality of life Questionnaire (EORTC QLQ) Core 30 (C30) and EORTC QLQ Multiple Myeloma Module (MY20) scores will be administered and collected prior to study treatment on Day 1 of each cycle. Actual values and changes from baseline of QLQ-C30 and QLQ-MY20 scores will be summarized for each cycle with non-missing sample size (n), mean, standard deviation, median, minimum, and maximum. The summary statistics will be tabulated separately for following groups: subjects who ended treatment due to disease progression before the end of Cycle 6, subjects who ended treatment due to disease progression after the end of Cycle 6 but before the end of Cycle 12, subjects who have completed all 12 cycles, subjects who ended treatment with reasons other than "Disease progression" before the end of Cycle 12. For subjects who have completed all 12 cycles of treatment, the overall QLQ-C30 and QLQ-MY20 scores will be summarized by Cycle 1-6 versus Cycle 7-12.

Best overall response rates (minimal response [MR], partial response [PR], very good partial response [VGPR], complete response [CR], and stringent complete response [sCR]) will be summarized descriptively at the end of study, end of Cycle 6 and end of Cycle 12 respectively. Overall response rate will also be summarized descriptively with 95 % CI estimated using the Clopper-Pearson method at the end of study, end of Cycle 6 and end of Cycle 12 respectively. The rate of PFS at 1 year will be estimated using the Kaplan-Meier method and with 95% CI estimated by Greenwood's formula (Kalbfleisch and Prentice, 1980) with log-log transformation and will be summarized by number of prior lines (1 vs ≥2). Similarly, the best overall response and overall response rate will also be summarized by number of prior lines (1 vs ≥2).

All secondary efficacy endpoints will be based on full analysis set.

Date: 08 June 2018 Page 18 of 27

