**Date:** 20 May 2019 **Page 21 of 132** 

Table 2-1. Schedule of Activities

	Screening a b				Tre	eatr	nen	t P	erio	d				Safety	
	(up to			Су	cle	1-2				C	ycl	e 3-	12	FU c (30	
PROCEDURE	21 days before Day 1)	Day 1	2	8	9	15	16	22	23	1	8	15	21	[+3] days post last dose)	Notes
Bone Lesion Assessment b	х														Screening and will be repeated if worsening clinical symptoms suggest PD, or as clinically indicated. (see Section 12.8 for IMWG criteria)
Plasmacytoma evaluation b	х														See Section 9.2.2.3. Only required at screening in subjects if clinically suspected and to confirm response (if performed at screening, see Section 12.8 for IMWG criteria)
Bone marrow aspirate with FISH b	Х														Bone marrow aspirate is required at screening and to confirm a response of CR (see Section 12.8 for IMWG criteria). FISH is only required at screening.
CLINICAL OUTCOME ASSESSM	MENTS														
EORTC QLQ-C30		Х								Х				X	During treatment period, these
EORTC QLQ-MY20		Х								Х				Х	questionnaires must be completed on day 1 of each cycle prior to dosing.
Amgen Satisfaction and Convenience Questionnaire		x								x				Х	During treatment period, these questionnaires must be completed on day 1 of each cycle prior to dosing, starting with C2D1. Items 8-11 to be collected only once at end of treatment or at completion of the trial.

Page 4 of 7

**Protocol Number:** 20170596

**Date:** 20 May 2019 Page 22 of 132

Table 2-1. Schedule of Activities

	Screening a b				Tre	eatr	nen	t Pe	erio	d				Safety	
	(up to			Су	cle	1-2				С	ycl	e 3-′	12	FU c (30	
PROCEDURE	21 days before Day 1)	Day 1	2	8	9	15	16	22	23	1	8	15	21	[+3] days post last dose)	
STUDY TREATMENT															
Kd ARM															
Carfilzomib administration h		X	×	X	X	X	×			x	x	x			Cycle 1: 20 mg/m² on days 1 and 2; 56 mg/m² on days 8, 9, 15, and 16 Cycle 2: 56 mg/m² Cycles 3-12: 70 mg/m² For subjects with baseline hepatic function abnormalities (bilirubin or AST > ULN), see Section 7.1.1.2.1 for modification of the initial dose. For cycle 3, for subjects who were previously dose reduced, see Section 7.1.1.2 for starting dose.
Dexamethasone administration h		x	х	X	X	X	X	Xi	Xi	х	х	х			Cycles 1-2: 20 mg Cycles 3-12: 40 mg For subjects ≥ 75 years of age, see Section 7.4.1.2 for dose modification.

**Protocol Number:** 20170596

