#### 9.2.6 Clinical Outcome Assessments

# 9.2.6.1 European Organization for Research and Treatment of Cancer Quality-of-life Questionnaire Core 30 (EORTC QLQ-C30)

The European Organization for Research and Treatment of Cancer Quality-of-life Questionnaire Core 30 (EORTC QLQ-C30) is a questionnaire developed to assess the quality of life of cancer patients (Bjordal et al, 2000).

EORTC QLQ-C30 includes 30 items grouped into:

- five quality of life categories: physical, social, emotional, cognitive and role performance;
- three scales of symptoms: fatigue, pain, and nausea and vomiting;
- a global scale of quality-of-life and individual items related to the symptoms of the disease and its treatment; dyspnea, insomnia, loss of appetite, constipation, diarrhea and
- an item on economic impact

The responses to the scale items refer to "last week," with the exception of the subject's physical performance scale, where the timeframe involved is the present.

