2.1 Objectives and Endpoints

Objectives	Endpoints
Primary	
Describe tolerability and treatment safety of a Kd regimen (Kd 56 mg/m² [Kd56] twice weekly for cycles 1-6 followed by Kd 70 mg/m² [Kd70] once weekly for cycles 7-12) in subjects with relapsed or refractory multiple myeloma with 1-3 prior lines of therapy at study entry.	 Proportion of subjects completing 12 cycles of treatment Dose intensity defined as total actual dose divided by planned dose through cycle 12 or up to disease progression Treatment-emergent adverse events and serious adverse events
Secondary	
Describe treatment adherence by the Kd regimen (Kd56 twice weekly and Kd70 once weekly).	 Dose intensity in cycles 1-6 and cycles 7-12 defined as total actual dose divided by planned dose through cycle 6 or 12 or up to disease progression Dose reductions in cycles 1-6 and cycles 7-12
	 Treatment discontinuation for all reasons in cycles 1-6 and cycles 7-12
Assess subject health-related quality-of-life (HRQoL) with Kd56 twice weekly and Kd70 once weekly.	 European Organization for Research and Treatment of Cancer Quality-of-life Questionnaire (EORTC QLQ) Core 30 (C30) and EORTC QLQ Multiple Myeloma Module (MY20) scores through cycle 12 or up to disease progression EORTC QLQ-C30 and EORTC QLQ-MY20 scores for cycles 1-6 and cycles 7-12 in subjects completing 12 cycles of treatment

Date: 08 June 2018 Page 7 of 27

[MI god cor stri	sponse rate (minimal response R], partial response [PR], very od partial response [VGPR], mplete response [CR], and ingent complete response [sCR]).
12	ndmark response rate (MR, PR, SPR, CR and sCR) after 6 and cycles.
	ogression-free survival (PFS) at rear
	sponse rate and PFS by line of or therapy 1 vs \geq 2
Exploratory	

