3.1 Study Design

This is a phase 2, multicenter, open-label study in subjects with RRMM in US community oncology centers. Subjects with 1-3 prior lines of therapy at study entry are eligible to be screened for participation. Subjects refractory to their last line of treatment are eligible to participate as long as their last line of treatment did not include an IP. The study will consist of a screening period of up to 28 days, up to 12 cycles of treatment, and a 30-day safety follow-up period following the last dose of study drug.

During the treatment period, all subjects will be treated with Kd 20/56 mg/m² twice weekly for up to six 28-day cycles followed by up to Kd 70 mg/m² once weekly for another six 28-day cycles. After discontinuation of study drugs, subjects will be followed for 30 days for adverse events.

Date: 08 June 2018 Page 8 of 27

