When analyzing progression-free survival time (PFS), baseline will be defined as the day of enrollment. When analyzing all other analysis endpoints for subjects who received study treatment, baseline is the closest recorded measurement prior to the first dose of any study treatment. If a subject doesn't receive any study treatment, baseline is defined as the latest measurement on or prior to enrollment date. If multiple valid records are observed at the same date and time, the average of these values will be used.

Study Day 1

The first day of study treatment administration or the enrollment date for subjects who are not administered any dose of study treatment.

Study Day

The number of days from the study day 1 to a date of interest, inclusive:

Study day n = (date of interest - date of study day 1) + 1.

Date: 08 June 2018 Page 10 of 27

Unless otherwise specified, the timing of all study-related events, assessments, and interventions will be calculated relative to study day 1. Study day –1 will be the day before study day 1, and in general for assessments prior to study day 1, study day is defined as:

Study Day
$$n = (date of interest - date of Study day 1)$$

Relative Dose Intensity (%)

Relative Dose Intensity (%) of carfilzomib/dexamethasone is defined as

Relative Dose Intensity =
$$100 \times \frac{\text{Actual Dose Intensity}}{\text{Intended Dose Intensity}}$$

Actual dose intensity is the actual cumulative dose (mg/m2 for carfilzomib, mg for dexamethasone) divided by the duration of exposure (week). Intended dose intensity is the planned cumulative dose (mg/m2 for carfilzomib, mg for dexamethasone) divided by the protocol specified treatment duration (week). Specifically,

- Actual cumulative dose is the sum of actual doses that a subject received. For carfilzomib, it is the sum of received doses (mg) divided by baseline BSA (m²). If BSA is > 2.2 m², then 2.2 will be used in the calculation. For dexamethasone, it is the sum of received doses (mg).
- Duration of exposure (week) is calculated as (Last Dose Date First Dose Date + Interval (days) to next planned treatment) / 7. Depending on the cycle and day of the last infusion, Interval (days) to next planned treatment is specified in following table:

			Interval (days) to Next
		Interval (days) to Next	Planned
	Cycle Day of the Last	Planned Carfilzomib	Dexamethasone
Last Cycle	Administration	Administration	Administration
1 - 6	Day 1 or Day 8	7	7
	Day 2 or Day 9	6	6
	Day 15	14	7
	Day 16	13	6

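### The SAP's quality-of-life contrast of cycles 1-6 with cycles 7-12 groups pre-dose Day 1 scores by visit, so each block holds one score from the preceding period

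*SAP*

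**What the plan says.** SAP 2.1 lists a secondary objective, "Assess subject health-related quality-of-life (HRQoL) with Kd56 twice weekly and Kd70 once weekly", and gives as one of its endpoints "EORTC QLQ-C30 and EORTC QLQ-MY20 scores for cycles 1-6 and cycles 7-12 in subjects completing 12 cycles of treatment". SAP 3.1 ties those blocks to the two dosing schedules: "all subjects will be treated with Kd 20/56 mg/m² twice weekly for up to six 28-day cycles", followed by six cycles once weekly. SAP 9.5.2 carries the endpoint into the analysis: for 12-cycle completers, "the overall QLQ-C30 and QLQ-MY20 scores will be summarized by Cycle 1-6 versus Cycle 7-12".

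Four other statements fix what each score measures.

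- **Timing.** SAP 9.5.2: the "scores will be administered and collected prior to study treatment on Day 1 of each cycle". Protocol Table 2-1 agrees: "questionnaires must be completed on day 1 of each cycle prior to dosing". The table also marks both questionnaires at the safety follow-up visit, 30 (+3) days after the last dose.
- **Baseline.** SAP Section 5: "baseline is the closest recorded measurement prior to the first dose of any study treatment". The C1D1 questionnaire is therefore the baseline.
- **Recall.** Protocol 9.2.6.1: "The responses to the scale items refer to" the last week, except physical performance, which refers to the present. Protocol Appendix 16 also gives the past week.
- **Version.** SAP Section 1 implements the protocol of 06 March 2018. Protocol Amendment 4 has two twice-weekly and then ten once-weekly cycles. Its Section 10.3.2.2 summarizes the scores by cycle, with no comparison of phases.

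**The concern.** A form completed before the first dose of a cycle cannot describe that cycle. It describes the end of the one before, or no treatment at all in the case of C1D1. If scores are pooled by the cycle number of the visit, the twice-weekly block contains the untreated baseline and the once-weekly block contains a score that belongs to twice-weekly dosing.

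This contrast is the SAP's direct summary of quality of life under the two schedules, and the convenience of once-weekly dosing is a main part of the study's rationale. A reader will take the difference between blocks as the difference between schedules. It is in fact a mixture of that difference and the change from baseline on starting treatment.

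**Working it through.** The plan gives no power, precision or expected mean for this contrast, so there is no figure to reproduce. The check counts visits.

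**Step 1: assign each Day 1 score to the regimen of the cycle just completed.** B is the untreated mean, T the mean under twice-weekly dosing and W the mean under once-weekly dosing.

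| Regimen | Visits C1D1 to C6D1 | Visits C7D1 to C12D1 |
|---|---|---|
| 6+6 (SAP) | 1 B, 5 T | 1 T, 5 W |
| 2+10 (Amendment 4), same cut | 1 B, 2 T, 3 W | 6 W |

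C7D1 is a clear case. Its recall week is cycle 6, days 22-28, and SAP Section 5 schedules dexamethasone on days 22 and 23 of that cycle.

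**Step 2: what the contrast estimates under 6+6.**

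(T + 5W)/6 - (B + 5T)/6 = (5W - 4T - B)/6 = (5/6)(W-T) + (1/6)(T-B)

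The error against W-T is (1/6)[(T-B) - (W-T)]. Changes from baseline give the same result: the blocks become 5(T-B)/6 and [(T-B) + 5(W-B)]/6, and their difference is unchanged.

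**Step 3: the same cut applied to 2+10.**

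W - (B + 2T + 3W)/6 = (3W - 2T - B)/6 = 0.5(W-T) + (1/6)(T-B)

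**Step 4: illustration over assumed values, in scale points.** The documents give none.

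| T-B | W-T (target) | 6+6 contrast | 2+10, cut at cycle 6 |
|---|---|---|---|
| -10 | +6 | 5.0 - 1.7 = +3.3 | 3.0 - 1.7 = +1.3 |
| -10 | +10 | 8.3 - 1.7 = +6.7 | 5.0 - 1.7 = +3.3 |
| -10 | 0 | -1.7 | -1.7 |
| -5 | +5 | 4.2 - 0.8 = +3.3 | 2.5 - 0.8 = +1.7 |
| 0 | +5 | +4.2 | +2.5 |
| +5 | +5 | 4.2 + 0.8 = +5.0 | 2.5 + 0.8 = +3.3 |
| +5 | 0 | +0.8 | +0.8 |

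Under 6+6 the sign reverses only if T-B and W-T have opposite signs and T-B is more than five times as large as W-T in absolute value.

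**Step 5: cycle 12.** The C12D1 score reflects cycle 11. With the last Kd dose on C12D15, safety follow-up falls on days 15 + 30 = 45 to 15 + 33 = 48, counted from C12D1. For a day 45 visit the recall week is days 38-44, after the 28-day cycle has ended. No score reflects cycle 12 treatment.

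**The case against.** The strongest reply is that the SAP never states how a score is attributed to a block. It does not define the overall scores, say whether values or changes are pooled, or say that the baseline record enters the first block. On that view this is missing detail. But grouping by visit cycle is the plain reading, no rule excludes C1D1 or moves C7D1, and pooling values or changes gives the same bias. Followed as written, the grouping gives the wrong contrast.

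Several limits do stand.

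- SAP 9.5.2 also tabulates actual values and changes for each cycle, separately for 12-cycle completers. A reader can see C1D1, C7D1 and C8D1 there. That exposes the problem but does not correct the pooled summary.
- The last week of a cycle follows the last carfilzomib dose (day 16 or day 15), so every Day 1 score describes a week without carfilzomib. Reassigning scores does not change that.
- The contrast is secondary, descriptive and limited to completers. No error rate or sample size depends on it.

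Two stronger readings are tempting. A reader might infer that, for current subjects, half of the twice-weekly scores are untreated baseline and the contrast becomes 0.9(W-T) + 0.5(T-B). That requires comparing cycles 1-2 with cycles 3-12, and neither document plans such a quality-of-life comparison. A reader might also infer that direction and size are distorted whatever the data. The formula says otherwise: under 6+6 there is no error when T-B = W-T, and in the first row of the table the direction is preserved.

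**Conclusion.** The point holds for the SAP as written. Under its 6+6 regimen the contrast estimates (5/6)(W-T) + (1/6)(T-B). It shrinks the schedule difference by one sixth and adds one sixth of the change from baseline. With T-B = -10, a true +6 appears as +3.3 and a true zero as -1.7.

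The weights assume that all 12 Day 1 forms are present, that the mean is stable within each phase, and that each score belongs to the cycle just finished. The point values are assumptions.

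Under 2+10 the more basic fault is that the cut at cycle 6 no longer separates the schedules: half of the first block is already once-weekly. The 6+6 split still fits the Kd subjects whom Protocol 7.1.1.2 keeps on the Amendment 2 regimen. The correction is worth making before database lock, although the consequence is limited to a descriptive secondary summary.

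**What to change.** State a visit-to-period rule in SAP 9.5.2, and align the endpoint in SAP 2.1 with it.

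- Use C1D1 only as baseline.
- Assign every later Day 1 score to the regimen of the cycle just completed.
- For subjects on 6+6, contrast C2D1-C7D1 (six scores) with C8D1-C12D1 (five scores). This estimates W-T.
- For subjects on 2+10, either delete the phase contrast to match the current protocol or, if it is kept, compare C2D1-C3D1 with C4D1-C12D1.
- Report the safety follow-up score separately as post-treatment.
- Note as a limitation that no score reflects cycle 12 treatment. Reassignment cannot cure this, because the data are not collected.

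The by-cycle tables can keep their Day 1 visit labels. The cost is SAP wording and a visit mapping in the programs, with no new data. Protocol 10.3 has the SAP finalized before database lock, which leaves room for the change.
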